8.4 SAE/AESI Report Form

SAEs/AESIs will be recorded on the FDA Form 3500A (MedWatch) but should only be reported as instructed below. The electronic FDA SAE reporting forms should not be used.

8.5 Reporting Procedures for Serious Adverse Events and AESIs

For the purposes of safety reporting, all adverse events will be reported that occur on or after Cycle 1 Day 1 through the End of Treatment Response Assessment. Adverse events, both serious and non-serious, and deaths that occur during this period will be recorded in the source documents. All SAEs/AESIs should be monitored until they are resolved or are clearly determined to be due to a subject's stable or chronic condition or intercurrent illness(es). Related AEs will be followed until resolution to baseline or grade 1 or stabilization.

8.5.1 SAE/AESI Reporting Requirements

- Participating investigators (all sites) must report all serious adverse events and AESIs to the Lead Site Principal Investigator (e.g. Sponsor-Investigator) within **1 business day** of discovery or notification of the event. The participating investigator must also provide follow-up information on the SAE/AESI until final resolution.
 - Please send all SAE/AESI reports to [contact] and cc: [contact] and the study coordinator listed on page 2.
- The Lead Site Principal Investigator will review the SAE and report the event to the FDA, external collaborator(s), and Cleveland Clinic IRB as applicable.
- It is the Sponsor-Investigator's responsibility (e.g. lead site PI) to ensure that ALL serious adverse events that occur on the study (e.g. ALL SAEs that occur at each enrolling institution) are reported to all participating sites.

Drug Supplier / Manufacturer / Financial Supporter Reporting Requirements:

- The investigator is responsible for ensuring that all AEs and SAEs/AESIs that are observed or reported during the study, as outlined in the prior sections, are recorded on the CRF
- It is the responsibility of the Sponsor-Investigator (Cleveland Clinic Principal Investigator) to report safety data to the drug supplier (AstraZeneca Data Entry Site [DES]).
- The Sponsor will submit appropriate reports to applicable local regulatory agencies and to ethics committees (ECs) as per local regulations. The Sponsor will notify Acerta Pharma/AstraZeneca in parallel with submission to the IRB (if applicable) and concerned Regulatory Authority for Suspected Unexpected Serious Adverse Reactions (SUSARs) and within fifteen (15) calendar days of awareness for other SAEs or Special Situation Reports using Form FDA 3500A (MedWatch). New information will be submitted to Acerta Pharma/AstraZeneca within the same time frame as initial reports.
- Whenever possible, SAEs should be reported by diagnosis term not as a constellation of symptoms.
- Death due to disease progression should be recorded on the appropriate form in the electronic data capture (EDC) system. If the primary cause of death is disease progression, the death due to disease progression should not be reported as an SAE to Acerta Pharma/AstraZeneca. If the primary cause of death is something other than disease progression, then the death should be reported as an SAE with the primary cause

of death as the event AE term, as death is typically the outcome of the event, not the event itself. The primary cause of death on the autopsy report should be the term reported. Autopsy and postmortem reports will be forwarded if readily available to Acerta Pharma/AstraZeneca DES as outlined above.

- If study drug is discontinued because of an SAE/AESI, this information must be included in the SAE report.

All SAEs/AESIs will be submitted by the lead site to the AstraZeneca Product Safety mailbox: [contact]

Institutional Review Board Reporting Requirements:

- Investigative sites will report adverse events to their respective IRB according to the local IRB's policies and procedures in reporting adverse events.

Pregnancy

Investigators should report all pregnancies and pregnancies in the partners of subjects to the Sponsor within 24 hours. The Sponsor should report any occurrences to the Cleveland Clinic IRB and Regulatory Authorities per institutional and/or regulatory guidelines, and to Acerta Pharma/AstraZeneca per contractual guidelines. Each participating site should follow their local institutional IRB reporting policies.

Any uncomplicated pregnancy that occurs with the subject or with the partner of a treated subject during this study will be reported. All pregnancies and partner pregnancies that are identified during or after the last dose of study medication will be reported, followed to conclusion, and the outcome reported.

Subjects should be instructed to immediately notify the investigator of any pregnancies. Any female subjects receiving study drug who become pregnant must immediately discontinue study drug. The investigator should counsel the subject, discussing any risks of continuing the pregnancy and any possible effects on the fetus.

Overdose

Clinical information relevant to overdose is not available. For results from nonclinical overdose studies in rats and dogs, please refer to the Investigator Brochure.

Study drug overdose is the accidental or intentional use of the drug in an amount higher than the dose being studied. An overdose or incorrect administration of study drug is not an AE unless it results in untoward medical effects.

Any study drug overdose or incorrect administration of study drug should be noted on the appropriate CRF and the sponsor-investigator should be notified immediately.

8.6 SAEs and OnCore

- All SAEs will be entered into OnCore.
- A copy of the SAE form(s) submitted to the sponsor-investigator is also uploaded into Oncore.

8.7 Data Safety and Toxicity Committee

It is the responsibility of each site PI to ensure that ALL SAEs occurring on this trial (internal or external) are reported to the Case Comprehensive Cancer Center's Data and Safety Toxicity Committee. This submission is simultaneous with their submission to the sponsor and/or other regulatory bodies.

The sponsor-investigator is responsible for submitting an annual report to the DSTC as per CCCC Data and Safety Monitoring Plan.

8.8 Data and Safety Monitoring Plan (DSMP)

This protocol will adhere to the policies of the Case Comprehensive Cancer Center Data and Safety Monitoring Plan in accordance with NCI guidelines.

9.0 PHARMACEUTICAL INFORMATION

A list of the adverse events and potential risks associated with the investigational or commercial agents administered in this study can be found in Sections 8.1 and 8.2.

9.1 Acalabrutinib

Other Names: ACP-196

Product description: Acalabrutinib capsules for oral administration, are supplied as yellow and blue, opaque hard gelatin capsules, 100 mg strength (size 1), and with acalabrutinib as an active ingredient. Each capsule also contains compendial inactive ingredients: silicified microcrystalline cellulose, which is composed of microcrystalline cellulose and colloidal silicon dioxide, partially pregelatinized starch, sodium starch glycolate, and magnesium stearate. The capsule shell contains gelatin, titanium dioxide, yellow iron oxide and indigotine (FD&C Blue 2).

Storage requirements: Acalabrutinib capsules are packaged in white, high-density polyethylene bottles and should be stored according to the storage conditions as indicated on the label. The recommended storage condition for acalabrutinib capsules is below 86°F.

Route of administration: Oral administration

Drug Procurement: Acalabrutinib will be supplied for this study by Acerta Pharma.

Drug Accountability: The investigator or designated study personnel are responsible for maintaining accurate dispensing records of the study drug. All study drugs must be accounted for, including study drug accidentally or deliberately destroyed. Under no circumstances will the investigator allow the investigational drug to be used other than as directed by the protocol. If appropriate, drug storage, drug dispensing, and drug accountability may be delegated to the pharmacy section of the investigative site.

Drug Destruction: At the completion of the study, there will be a final reconciliation of drug shipped, drug consumed, and drug remaining. This reconciliation will be logged on the drug reconciliation form, signed and dated. Any discrepancies noted will be investigated, resolved, and documented prior to return or destruction of unused study drug. Drug destroyed on site will be documented in the study files.

9.2 Rituximab

Other Names: Rituxan™, Mabthera™

Product description: Rituximab is a sterile, clear, colorless, preservative-free liquid concentrate for intravenous (IV) administration. The product is formulated for intravenous administration in 9.0 mg/mL sodium chloride, 7.35 mg/mL sodium citrate dihydrate, 0.7 mg/mL polysorbate 80, and Sterile Water for Injection. The pH is adjusted to 6.5. Rituximab biosimilar use is permitted for this study per treating investigator discretion or per insurance mandate.

Solution preparation: Using appropriate aseptic technique, withdraw the necessary amount of rituximab and dilute to a final concentration of 1 to 4 mg/mL into an infusion bag containing either 0.9% Sodium Chloride or 5% Dextrose in Water. Gently invert the bag to mix the solution. Discard any unused portion left in the vial. Caution should be taken during the preparation of the drug, as shaking can cause aggregation and precipitation of the antibody. Do not mix or dilute with other drugs.

Storage requirements: Once reconstituted into IV bags, rituximab is chemically stable for up to 24 hours at 2°C to 8°C (36°F to 46°F), followed by up to 24 hours at room temperature (23°C). However, since rituximab solutions do not contain preservative, diluted solutions should be stored refrigerated (2°C to 8°C). No incompatibilities between rituximab and polyvinylchloride or polyethylene bags have been observed. Rituximab vials should be protected from direct sunlight.

Stability: Rituximab is biologically and chemically stable at 2°C to 8°C (36°F to 46°F) and has a proposed shelf life stability of 30 months. Rituximab vials are intended for single use only. Do not use beyond the expiration date stamped on the carton.

Route of administration:

DO NOT ADMINISTER AS AN INTRAVENOUS PUSH OR BOLUS. Do not infuse rituximab concurrently with another IV solution or other IV medications. Premedication, consisting of acetaminophen 650 mg to 1000 mg PO and diphenhydramine 25 to 50 mg IV or PO, will be administered before each infusion of rituximab. Premedication may attenuate infusion-related events. Since transient hypotension may occur during rituximab infusion, anti-hypertensive medications will be withheld 12 hours prior to rituximab infusion.

Rituximab will be administered intravenously per institutional standard. An in-line filter is not required.

Rituximab infusion must be interrupted for severe reactions. If the patient experiences fever and rigors, the antibody infusion is discontinued. The severity of the side effects will be evaluated. In most cases, the infusion can be resumed at a 50% reduction in rate (e.g., from 100mg/hr to 50mg/hr) when symptoms have completely resolved. Most patients who have experienced non-life-threatening infusion-related reactions have been able to complete the full course of rituximab therapy.

NOTE: In addition, alternative rituximab infusion rates (i.e., “rapid rituximab infusion”) can be used per institutional guidelines as long as the total number of milligrams of rituximab is the

same and that “rapid infusion” is not administered with the patient’s first rituximab cycle. Further, a rituximab infusion time should not be less than 90 minutes in duration.

9.3 Rituximab-hyaluronidase human

Other names: Rituxan Hycela, MabThere S.C.

Product Description: rituximab-hyaluronidase injection is a colorless to yellowish, clear to opalescent solution supplied in sterile, preservative-free, single-dose vials for subcutaneous administration. Each mL of solution contains rituximab (120 mg), hyaluronidase human (2,000 Units), L-histidine (0.53 mg), L-histidine hydrochloride monohydrate (3.47 mg), L-methionine (1.49 mg), polysorbate 80 (0.6 mg), α,α -trehalose dihydrate (79.45 mg), and Water for Injection.

Solution Preparation: Draw up 11.7 mL of rituximab-hyaluronidase injection into a syringe. To avoid clogging, attach administration needle, or catheter, only when the patient is ready for injection.

Storage Requirements: Vials should be stored in the refrigerator at 2°C–8°C (36°F–46°F) in the original carton to protect from light. Do not freeze.

Stability: If not used immediately, prepared syringe may be stored in the refrigerator at 2-8°C for up to 48 hours and subsequently for 8 hours at room temp up to 30°C

Route of administration: Patient must have received at least one dose of rituximab IV, without serious infusion reaction, before starting rituximab- hyaluronidase. DO NOT ADMINISTER AS AN INTRAVENOUS PUSH OR BOLUS. Premedicate patients with acetaminophen 650mg and diphenhydramine 50mg, prior to each dose.

The dose should be administered over 5 minutes, into the subcutaneous tissue of the abdomen. Never inject into areas where the skin is red, bruised, tender or hard, or areas where there are moles or scars. If administration is interrupted, continue administering at the same site, or at a different site, but restricted to the abdomen. Patients must be observed for at least 15 minutes following administration.

Drug Procurement: Rituximab must be obtained from commercial sources.

10.0 CORRELATIVE STUDIES

10.1 Tissue Procurement

The following materials should be sent for each patient that signs consent. The slides should be done after the patient has signed the consent form to participate in the study and within 4 weeks of starting study treatment.

1. Fifteen 4 micron unstained sections on charged (plus) slides
2. Four 10 micron sections (if an incisional or excisional biopsy) or eight 10 micron sections (if needle biopsy) on slides or in a tube

10.2 Blood Sample

20 ml of peripheral blood will be obtained at the time of sample collection (baseline, after C1, and then end of treatment) in heparinized green top tubes.

The green top heparin tubes will be processed into aliquots of plasma and viable mononuclear cells.

10.3 Shipment

Please ship the slides/tube to the Cleveland Clinic Biorepository at the address provided below:

Robert J. Tomsich Pathology and Laboratory Medicine Institute (RT-PLMI)

ATTN: [name]

[name]

[name]

Please ship the blood samples to the Cleveland Clinic Pharmacology Lab. The Manual of Operating Procedures (MOP) contains more detailed instructions on shipment of the slides and blood samples.

Information about the planned analyses concerning these correlative studies will be added in a protocol amendment.

11.0 STUDY PARAMETERS AND CALENDAR

11.1 Study Parameters

11.1.1 Screening Evaluation day -28 to 1

Screening studies and evaluations will be used to determine the eligibility of each subject for study inclusion. All evaluations must be completed ≤ 28 days prior to administration of protocol therapy, except where otherwise indicated.

- Informed Consent
- Demographics
- Medical History
- Physical Examination
- IPI score
- Height
- Weight
- Vital signs including: blood pressure, pulse, respiratory rate and temperature.
- Concurrent Medications Assessment including prescription medications, over-the-counter (OTC) medications and supplements.
- ECOG Performance Status
- Urinalysis
- Baseline Symptoms Assessment
- Complete Blood Count (CBC) with differential
- PT/INR

- Serum chemistry panel: sodium, potassium, chloride, bicarbonate, BUN, creatinine, calcium, glucose, total protein, albumin, alkaline phosphatase, total bilirubin, SGOT [AST], and SGPT [ALT]
- Lactate dehydrogenase (LDH) level, uric acid, phosphorus
- Pregnancy test for women of childbearing potential (within 72 hrs of study of study treatment). Women who have undergone surgical sterilization or who have been postmenopausal for at least 2 years are not considered to be of childbearing potential.
- Peripheral blood Epstein Barr Virus (EBV) PCR (if not done within 1 month of diagnosis)
- Remote Hepatitis Panel (Hepatitis B Surface Antigen, Hepatitis B Surface Antibody, Hepatitis B Core Antibody, Hepatitis C antibody)* (no need to repeat if done within 3 months of start of study treatment)
- HIV (no need to repeat if done within 3 months of start of study treatment)
- Electrocardiogram (EKG)
- PET and CT scan of neck, chest, abdomen, and pelvis with IV and PO contrast. Neck CT can be omitted at the investigator's discretion, if no suspicion for involvement. If insurance only allows one type of scan, PET scan is preferred at baseline.
- Bone marrow aspiration and biopsy. This can be omitted at investigator's discretion, if there is low or no suspicion of involvement
- Send tumor biopsy slides to CCF for correlative studies. Biopsy slides should be sent within 4 weeks of start of study treatment. Please see section 10 for detailed information. If tissue is not available, approval from the sponsor-investigator must be received.
- Peripheral blood sample for correlative studies

*** Hepatitis B and C Testing**

Hepatitis serology testing must include hepatitis B surface antigen (HBsAg), hepatitis B surface antibody (anti-HBs), anti-HBc, and HCV antibody. In addition, any subjects testing positive for any hepatitis serology must have PCR testing during screening. Subjects with a known history of hepatitis C should be tested for HCV RNA during screening and monthly. See exclusion criterion 4.2.17.

Subjects who are anti-HBc positive should have quantitative PCR testing for HBV DNA performed during screening and may be repeated as per institutional practices. Patients with detectable viral load are not eligible for participation.

11.1.2 Treatment Period

Cycle 1 is 28 days followed by interim response assessment at day 42 (- 3 day window)

Cycle 2 (in patients with CR is 28 days)

Cycles 2-4 (in patients with PR is 28 days)

Cycle 1, Day 1

- Physical Examination
- Weight
- Vital signs including: blood pressure, pulse, respiratory rate and temperature.
- Concurrent Medications Assessment including prescription medications, over-the-counter (OTC) medications and natural/herbal supplements.
- ECOG performance status
- Laboratory Studies:
 - Complete Blood Count (CBC) with differential and platelets.

- Serum Chemistries: Serum chemistry panel: sodium, potassium, chloride, bicarbonate, BUN, creatinine, calcium, glucose, total protein, albumin, alkaline phosphatase, total bilirubin, SGOT [AST], SGPT [ALT]
 - LDH, uric acid, phosphorous
- Rituximab IV administration
- Acalabrutinib started (days 1 – 28)
- Adverse event evaluation and documentation

Cycle 1, Day 8 ± 2 days

- Vital signs including: blood pressure, pulse, respiratory rate and temperature.
- Laboratory Studies:
 - Complete Blood Count (CBC) with differential
- Rituximab administration
- Adverse event evaluation and documentation

Cycle 1, Day 15 ± 2 days

- Vital signs including: blood pressure, pulse, respiratory rate and temperature.
- Laboratory Studies:
 - Complete Blood Count (CBC) with differential
 - Serum Chemistries: Serum chemistry panel: sodium, potassium, chloride, bicarbonate, BUN, creatinine, calcium, glucose, total protein, albumin, alkaline phosphatase, total bilirubin, SGOT [AST], SGPT [ALT]
- Rituximab administration
- Adverse event evaluation and documentation

Cycle 1, Day 22 ± 2 days

- Vital signs including: blood pressure, pulse, respiratory rate and temperature.
- Laboratory Studies:
 - Complete Blood Count (CBC) with differential
- Rituximab administration
- Adverse event evaluation and documentation

Cycle 1, Day 42 (-3 day window)

- CT scan of neck, chest, abdomen, and pelvis with IV and PO contrast. CT neck can be omitted if there was no involvement at baseline
- Interim disease response assessment
- Peripheral blood EBV PCR if positive at baseline
- Adverse event evaluation and documentation
- Peripheral blood sample for correlative studies

Cycle 2, Day 1 (for CR responders ONLY)

Cycle 2 should start within 2 weeks after the end of cycle 1 treatment.

- Physical Examination
- Weight
- Vital signs including: blood pressure, pulse, respiratory rate and temperature
- Concurrent Medications Assessment including prescription medications, over-the-counter (OTC) medications and natural/herbal supplements.
- ECOG Performance Status
- Adverse event evaluation and documentation

- Laboratory Studies:
 - Complete Blood Count (CBC) with differential and platelets
 - Serum Chemistries: Serum chemistry panel: sodium, potassium, chloride, bicarbonate, BUN, creatinine, calcium, glucose, total protein, albumin, alkaline phosphatase, total bilirubin, SGOT [AST], SGPT [ALT]
 - Lactate dehydrogenase (LDH)
- Rituximab administration on days 1, 8, 15, and 22
- Acalabrutinib on days 1-28

Cycles 2-4, Day 1 (for PR responders ONLY)

Cycle 2 should start within 2 weeks after the end of cycle 1 treatment. There is a \pm 3 day window for the start of cycles 3 and 4.

- Physical Examination
- Weight
- Vital signs including: blood pressure, pulse, respiratory rate and temperature
- Concurrent Medications Assessment including prescription medications, over-the-counter (OTC) medications and natural/herbal supplements.
- ECOG Performance Status
- Adverse event evaluation and documentation
- Laboratory Studies:
 - Complete Blood Count (CBC) with differential and platelets
 - Serum Chemistries: Serum chemistry panel: sodium, potassium, chloride, bicarbonate, BUN, creatinine, calcium, glucose, total protein, albumin, alkaline phosphatase, total bilirubin, SGOT [AST], SGPT [ALT]
 - Lactate dehydrogenase (LDH) only on cycle 2 day 1 (not required on cycles 3-4)
- Rituximab administration on day 1
- Acalabrutinib started (continue days 1-28)

End of Treatment Response Assessment – 8 weeks \pm 7 days after treatment completion (this

visit does not apply to subjects with stable/progressive disease after cycle 1)

- Physical Examination
- Weight
- Vital signs including: blood pressure, pulse, respiratory rate and temperature.
- Concurrent Medications Assessment including prescription medications, over-the-counter (OTC) medications and natural/herbal supplements.
- ECOG Performance Status
- Adverse Event Evaluation
- Laboratory Studies:
 - Complete Blood Count (CBC) with differential and platelets.
 - Serum Chemistries: albumin, alkaline phosphatase, total bilirubin, bicarbonate, BUN, calcium, chloride, creatinine, glucose, potassium, total protein, SGOT [AST], SGPT [ALT], sodium
 - Lactate dehydrogenase (LDH)
 - Peripheral blood EBV PCR if positive at baseline
- PET and diagnostic CT of neck, chest, abdomen, and pelvis with IV and PO contrast for response assessment. Neck CT can be omitted if no involvement at baseline. If insurance only allows one type of scan, PET scan is preferred for end of treatment assessment.
- Disease response assessment

- Bone marrow aspiration and biopsy if positive at baseline
- Peripheral blood sample for correlative studies

Duration of Follow Up

After completion of the study treatment the subjects will be followed for a total of 3 years. The follow up visits will be done at 6, 12, 18, 24 and 36 months after the last cycle of therapy. There is a \pm 14 day window for these visits. If the patient is unable to follow up in person, virtual visits may be used to capture applicable procedures during long-term follow up only.

The follow up visits should include the following:

- Survival/Disease Status
- Physical Examination
- Vital signs
- CBC with differential
- Serum chemistry panel
- Diagnostic CT neck, chest, abdomen and pelvis scan with IV and PO contrast will be done at 6, 12 and 24 months if no disease progression. Neck CT can be omitted if no involvement at baseline
- Peripheral blood EBV PCR if positive at baseline will be done at 6, 12 and 24 months
- Current lymphoma treatment

Patients who have stable/progressive disease are not required to come in for clinical follow up. These patients can be contacted over the phone by the study personnel to obtain the following information

- Survival/Disease Status
- Current lymphoma treatment

Patients will be followed for toxicity until the End of Treatment Response Assessment study visit or until death, whichever occurs first. The clinical course of each event will be followed until resolution, stabilization, or until has been determined that the study treatment or participation is not the cause.

Serious adverse events (SAE) that are still ongoing at the end of the study period will necessitate follow-up to determine the final outcome. Any serious adverse event that occurs after the study period and is considered to be possibly related to the study treatment or study participation will be recorded and reported immediately.

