6.5 Duration of Follow Up

End of Treatment Response Assessment: End of treatment scans and visit will be completed within 8 weeks (± 7 days) of treatment termination. Subjects with stable or progressive disease after Cycle 1 Day 36 scans will go directly onto LTFU.

If there is an adverse event related to study drug, the clinical course of each event will be followed until resolution, stabilization, or until it has been determined that the study treatment or participation is not the cause with a cut off of 24 months after completion of therapy.

Serious adverse events that are still ongoing at the end of the study period will necessitate follow-up to determine the final outcome. Any serious adverse event that occurs after the study period and is considered to be possibly related to the study treatment or study participation will be recorded and reported immediately.

Long-Term Follow Up

Each subject should be followed for a total of 3 years after study treatment has ended. Follow up visits will occur at 6, 12, 18, 24 and 36 months after completion of treatment. During this period, subjects will be followed via physical exam and laboratory analysis. CT scans will be repeated at 6, 12, and 24 months. If the patient is unable to follow up in person, virtual visits may be used to capture applicable procedures during long-term follow up only. Subjects who

experience disease progression are not required to come in for clinic follow up. Study team will make every effort to contact them via phone to obtain information specified in the protocol (see section 11.1.2).

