11.2 Calendar

Procedures	Screening	Cycle 1					Cycles 2-4 ^f	End of Treatment	Long Term Follow Up (± 14 days) ^h				
	Day -28 to Day 1	Day 1 ⁱ	Day 8 (± 2)	Day 15 (± 2)	Day 22 (± 2)	Day 42 (-3)	Day 1	8 weeks ± 7 days after treatment completion	6 Months	12 Months	18 Months	24 Months	36 Months
Medical History	X												
Physical Exam	X	X					X	X	X	X	X	X	X
Vital Signs ^o	X	X	X	X	X		X	X	X	X	X	X	X
Height/Weight	X	X					X	X					
Concurrent Meds Assessment	X	X					X						
Baseline Symptom Assessment	X												
Adverse Event Evaluation		X	X	X	X	X	X	X					
Tumor Tissue	X												
Peripheral Blood Sample	X					X		X					
ECOG Status	X	X					X	X					
CBC w/ differential	X	X	X	X	X		X	X	X	X	X	X	X
PT/INR	X												
Serum Chemistry ^a	X	X		X			X	X	X	X	X	X	X
LDH	X	X					X ^j	X					
Uric acid and phosphorous	X	X											
Pregnancy Test	X ^g												
Urinalysis	X												
Hepatitis Panel	X												
HIV testing	X												
EBV PCR	X ^j				X ^k		X ^k	X ^k	X ^k			X ^k	
ECG	X												
CT Neck/Chest/Abdomen/Pelvis ^c	X ^b				X ^e		X ^e	X ^e	X ^e			X ^e	
PET Scan ^c	X						X						

Bone marrow biopsy/aspiration	X^m							Xⁿ					
Disease Response Assessment						X		X					
Acalabrutinib ^d		X					X						
Rituximab		X	X	X	X		X						
Survival/Disease Status									X	X	X	X	X

- a. Sodium, potassium, chloride, bicarbonate, BUN, creatinine, calcium, glucose, total protein, albumin, alkaline phosphatase, total bilirubin, SGOT [AST], SGPT [ALT]
- b. Neck CT can be omitted at baseline at the discretion of the investigator if there was no suspicion for involvement
- c. PET and diagnostic CT scan preferred, but PET alone is preferred, if unable to obtain both.
- d. Acalabrutinib given on days 1-28
- e. CT neck can be omitted if there was no baseline involvement
- f. For subject in a CR after cycle 1, rituximab will be administered on the same schedule as cycle 1 (see Table 2). For these patients, no other study assessment will be done on days 8, 15, and 22.
- g. Pregnancy test to be done within 72 hours of starting the study drug. This only applies to women of childbearing potential.
- h. Patients with disease progression only need to have survival follow-up and current lymphoma treatment captured (see section 11.1.2). Virtual visits may be used to capture applicable procedures during long-term follow up only if the patient is unable to follow up with the in person.

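### Section 11.1.2 lets stable-disease patients move to phone-only follow-up while four other statements do not, so their later progression may not be scan-documented and PFS is likely to be biased upward

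*Combined protocol and SAP*

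**What the plan says.** Five statements bear on who is scanned in long-term follow-up.

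- Section 11.1.2, paragraph on reduced follow-up: "Patients who have stable/progressive disease are not required to come in for clinical follow up". It continues: "These patients can be contacted over the phone by the study personnel to obtain the following information". The items listed are survival/disease status and current lymphoma treatment.
- Section 11.1.2, CT item in the list just above: the scans "will be done at 6, 12 and 24 months if no disease progression".
- Section 6.5: "Subjects with stable or progressive disease after Cycle 1 Day 36 scans will go directly onto LTFU". There, "CT scans will be repeated at 6, 12, and 24 months", and the patients excused from clinic are those who "experience disease progression are not required to come in for clinic follow up".
- Section 11.2, calendar footnote h: "Patients with disease progression only need to have survival follow-up and current lymphoma treatment captured".
- Section 12.0: CT at 6, 12 and 24 months after the last cycle, with no exemption for stable disease.

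Two further provisions matter. Section 11.1.2 waives the end-of-treatment visit, with its scans, for patients who are stable or progressing after cycle 1. Section 12.1.5 counts documented progression or death as a PFS event. It otherwise censors at the last assessment, including when non-protocol therapy has started.

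**The concern.** A patient with SD at the interim scan has not had a PFS event. One sentence in 11.1.2 treats this patient like a progressor for follow-up purposes, and the other four statements do not. Section 6.5 and footnote h both send the reader to 11.1.2 for detail, so a site that follows the cross-reference arrives at the broader exemption. No rule says which text prevails.

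What is at stake is how PFS is ascertained in patients whose disease did not respond and whose study treatment has stopped. If they are no longer scanned, censoring is tied to poor prognosis, and the Kaplan-Meier curve leans on the responders. Sites could also handle identical patients differently, and scans not taken cannot be recovered at analysis.

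**Working it through.** The plan gives no figure on this point, so the check is mainly a comparison of texts.

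1. **Who is released from clinic and CT?**
   - 11.1.2, phone paragraph: stable and progressive disease.
   - 11.1.2, CT item: CT continues unless there is progression, so SD stays in.
   - 6.5: only progressors are released.
   - Footnote h: only progressors are reduced to survival and treatment data.
   - 12.0: CT at all three times, with no SD exemption.

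   One statement releases SD patients and four do not. Section 11.1.2 also disagrees with itself.

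2. **Protocol scans for an SD patient after the interim CT.** The end-of-treatment scan is waived, so it contributes 0 under either reading. Follow-up CTs number 0 under the phone paragraph and 3 (months 6, 12 and 24) under the other four statements. The difference is 3 scans per SD patient.

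3. **Date of the last scan under the phone paragraph.** Section 11.1.2 and the calendar put the interim CT at cycle 1 day 42 (minus 3 days). The Protocol Summary and section 3.4 say days 39-42 after the end of cycle 1 treatment, and section 6.5 still refers to day 36. The censoring date is therefore unsettled too, but the count of 0 against 3 does not depend on it.

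4. **Direction of the effect on PFS.** Let r, s and p be the proportions with response, SD and progression at the interim scan (r + s + p = 1). Let S_R and S_SD be 1-year PFS in responders and SD patients.
   - With SD fully observed: r × S_R + s × S_SD.
   - With every SD patient censored at the interim scan: (1 − p) × S_R.
   - Difference: s × (S_R − S_SD), which is positive whenever SD patients do worse than responders.

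5. **What would be needed for a size.** The documents give none of s, S_R or S_SD. As an illustration on assumed values only:
   - Take 25% to 40% non-responders (the complements of the 75% target and 60% null ORR), with 25% to 75% of them SD. Then s runs from 0.25 × 0.25 = 6.25% to 0.40 × 0.75 = 30%, or about 4 to 19 of 62 patients.
   - With S_R = 80% and S_SD = 20% to 50%, the difference runs from 0.0625 × 0.30 = 1.9 points to 0.30 × 0.60 = 18 points.
   - For each set of inputs this assumes that no SD patient ever contributes an event, so it is a ceiling and not an estimate.

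6. **What does not change.** ORR does not use the follow-up scans. The success rule reproduces by exact binomial: P(X ≥ 44 | n = 62, p = 0.60) = 0.049 and P(X ≥ 44 | n = 62, p = 0.75) = 0.812. It is untouched. DOR covers responders only, OS can be obtained by phone, and TTF already counts stopping treatment as failure.

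**The case against.** The conflict itself is hard to dispute, but several limits on its consequence stand.

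- **Phone contact is not silence.** It collects survival and disease status. A death before any new therapy remains a PFS event. Whether progression reported by phone counts as documented is not stated, and it is not excluded either. The fair wording is that progression may not be documented by scan.
- **Non-protocol therapy.** SD patients stop study treatment, and section 1.1 notes that inadequate response leads to added chemotherapy in a subset. Anyone who starts such therapy before the 6-month CT is censored at the interim scan whichever text governs, so aligning the text removes only part of any bias.
- **Intent.** The end-of-treatment waiver groups stable with progressive disease, and footnote h points to 11.1.2. The sponsor may have meant phone-only follow-up for both groups. This supports reconciling the texts but does not settle the direction.
- **Weight.** PFS is one of several secondary endpoints and has no target or success rule.

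A reader might go further in two ways. One is to infer that PFS loses all its non-responders at the interim scan. The documents do not support this: patients progressing at that scan are PFS events, and 11.1.2 only says that attendance is not required. The other is to attach a definite overstatement to this sentence. For example, SD in 10% to 20% of patients, responder PFS of 75% and SD PFS of 30% or 6% give 0.10 × 0.45 = 4.5 to 0.20 × 0.69 = 13.8 points. Those inputs are not in the documents. The sum also gives SD patients no events at all and attributes to this sentence censoring that section 12.1.5 would impose anyway.

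**Conclusion.** This is an internal inconsistency that should be corrected. Its certain effect is 0 against 3 protocol CTs after the interim scan for each SD patient, depending on which statement a site follows. Its likely effect is an upward bias in PFS, on the assumption that SD patients progress sooner than responders. The documents do not allow that bias to be sized, and the range in the working only shows how strongly it depends on assumed inputs. Only SD patients and only PFS are affected. The primary analysis and the other secondary endpoints stand.

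**What to change.** Reconcile the five statements. The smallest edit is to remove *stable/* from the phone-follow-up sentence in 11.1.2. Reduced follow-up would then begin after documented progression, matching 6.5, footnote h and the CT item in 11.1.2 and consistent with 12.0, and SD patients would keep the CTs already scheduled until progression.

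If the sponsor intends phone-only follow-up for SD, amend those four statements instead. In that case state in 12.1.5 how PFS treats these patients, including whether progression reported by phone counts as documented. Under either choice, give the interim scan a single date throughout.

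The cost of the smallest edit is a one-word amendment, plus clinic visits and up to three CTs per SD patient. Four of the five statements already require these, so the edit adds no scan beyond what they plan. It does not address censoring at non-protocol therapy, which remains.
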